If a medical adverse event should occur, study staff includes two physicians who are board-certified in psychiatry (Drs. [name] and [name]). Additional medical assistance will be available through the VA TMS clinical roll-out staff RN's and physicians trained in TMS safety and adverse event management, and VA Palo Alto HCS Emergency Department service is readily available, if needed. Immediate psychiatric/psychological consultation will available for participants if required ([name]: Licensed Clinical Psychologist and [name]: Board Certified Psychiatrist). Appropriate referrals will be made when necessary in the judgment of the PI/PD or study physician.

g) Lead Investigator or Coordinating Institution in Multi-site Study.

Please explain (i) your role in coordinating the studies, (ii) procedures for routine communication with other sites, (iii) documentation of routine communications with other sites, (iv) planned management of communication of adverse outcomes, unexpected problems involving risk to participants or others, protocol modifications or interim findings.

1. Purpose

a) In layperson's language state the purpose of the study in 3-5 sentences.

The purpose of this study is to evaluate the efficacy of intermittent theta burst (iTBS) transcranial magnetic stimulation (TMS) as a treatment for Veterans with an alcohol use disorder (AUD) to decrease the exceedingly high rate of relapse associated with this condition.

b) State what the Investigator(s) hope to learn from the study. Include an assessment of the importance of this new knowledge.

At least 60% of those with AUD will experience a major relapse period within 6 months of treatment, irrespective of the intervention

(psychosocial and/or pharmacological) employed. Consequently, the high prevalence of AUD and relapse following treatment in Veterans is associated with substantial resource allocation and costs for the DVA Health Care System. Current pharmacological and psychosocial interventions demonstrate only a moderate level of efficacy, which is reflected in the high rate of relapse in AUD.

iTBS-TMS is a neurostimulation method that is at the forefront of innovative, non-invasive, and safe treatments for AUD, and the disorders that commonly co-occur with AUD. To reduce the high rate of relapse in Veterans with AUD, it is necessary for interventions to more effectively address the associated neurobiological dysfunction and salient co-occurring conditions.

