Design, Treatment Phase and Treatment Arms: This is a double-blind randomized group design, which will enroll 40 participants. After screening and baseline procedures, participants will be randomized to active or sham iTBS-TMS conditions (20 active, 20 sham); thus participants will have a 50% probability of receiving active treatment. Participants will receive 20 iTBS-TMS sessions over the course of 2 weeks. Participants will be required to be abstinent from alcohol and illicit substance for 7 days and demonstrate no clinically significant withdrawal symptoms prior to randomization.

Rationale for Brain Region Site: The left dorsolateral prefrontal cortex (DLPFC) was chosen as the iTBS stimulation site given excitatory transcranial magnetic stimulation to this region has been demonstrated to decrease cravings in non-Veterans with AUD. Additional stimulation of this site has been robustly shown to be associated with decreased unipolar depressive symptomatology; depressive disorders are highly comorbid in Veterans with AUD.

Duration of Treatment Phase: Active iTBS-TMS Treatment Group – will receive a total of 20 treatments delivered 5 days/week, two treatments per day (Monday-Friday), over 2 consecutive weeks. Sham Treatment group will receive the same frequency and

duration of treatment, without actual administration of iTBS-TMS. iTBS-TMS sessions will be delivered prior to the beginning of participants' treatment day, and at lunch, as to not interfere with their treatment-as-usual in the VA substance treatment clinics. There have been no adverse events reported in the literature implementing two iTBS sessions per day in any population.

Procedures for Delivery of iTBS-TMS Sessions:

1) Anatomical localization of the left DLPFC for the stimulation coil will be individualized for each participant and achieved through standardized procedures for EEG electrode placement, optimized for transcranial magnetic stimulation. The localization of participant left DLPFC will be confirmed using the subject MRI data collected prior to the treatment phase.

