b) Please list in the table below all IDE Exempt Devices (Commercial Device used according to label, Investigational In Vitro Device or Assay, or Consumer Preference/Modifications/Combinations of Approved Devices) to be used on participants.

6. Drugs, Reagents, or Chemicals

a) Please list in the table below all investigational drugs, reagents or chemicals to be administered to participants.

b) Please list in the table below all commercial drugs, reagents or chemicals to be administered to participants.

7. Medical Equipment for Human Subjects and Laboratory Animals

If medical equipment used for human patients/participants is also used on animals, describe such equipment and disinfection procedures.

N/A

8. Participant Population

a) State the following: (i) the number of participants expected to be enrolled at Stanford-affiliated site(s); (ii) the total number of participants expected to enroll at all sites; (iii) the type of participants (i.e. students, patients with certain cancer, patients with certain cardiac condition) and the reasons for using such participants.

(i)(ii) &(iii): Forty (40) participants are expected to be enrolled (20 active iTBS-TMS and 20 sham

iTBS-TMS) from all substance abuse clinics at the VA Palo Alto, but primarily from the Foundations of Recovery (FOR) 30 day residential program.

b) State the age range, gender, and ethnic background of the participant population being recruited.

The study will be open to males and females, regardless of race and ethnic origin, 21-65 years of age, who are in active treatment for an AUD at the VA Palo Alto. The 21-65 age range was chosen given the vast majority of information on iTBS-TMS efficacy and safety has been obtained from this range and this is the typical age range of Veterans seeking treatment for AUD at the VA Palo Alto.

c) State the number and rationale for involvement of potentially vulnerable subjects in the study (including children, pregnant women, economically and educationally disadvantaged, decisionally impaired, homeless people, employees and students). Specify the measures being taken to minimize the risks and the chance of harm to the potentially vulnerable subjects and the additional safeguards that have been included in the protocol to protect their rights and welfare.

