Neuroimaging measure (e.g., Glu level) and treatment group (active iTBS-TMS vs. control) are the target predictors, with age as a covariate because it will likely account for significant within and between subject variance. Smoking, PTSD and/or substance use severities will be used as covariates if there are post-hoc differences between treatment groups on these variables after random assignment. We predict an interaction between the specific neuroimaging measure (e.g., Glu level) and treatment group; follow-up simple effect tests will indicate that participants in the active iTBS-TMS group with lower Glu concentration,

lower perfusion (blood flow), and smaller volume of the left DLPFC at baseline will show the longest duration of abstinence. Separate models will be run for each neuroimaging predictor to minimize the risk of overfitting and corresponding inflated Type I error. To control significance levels of main effects and interactions for multiplicity of tests, we will employ a modified Bonferroni procedure described in our previous studies .

Exploratory Hypothesis 1

1a) Veterans with co-occurring MDD, who receive active iTBS-TMS, demonstrate a significantly lower frequency of relapse over 6 months following treatment than controls (i.e. Veterans with co-occurring MDD who receive sham iTBS-TMS).

Statistical Approach: Exploratory Hypothesis 1a will be tested with binary logistic regression. The criterion/dependent measure is relapse status (abstained or relapsed during the 6 months after last iTBS-TMS session). Treatment group (active iTBS-TMS vs. control) is the target predictor, with antidepressant use (binary, yes/no) as a covariate. Education and severity of PTSD, substance use, and/or depressive symptomatology will be considered as covariates if, after random assignment, there are post-hoc differences between treatment groups on these variables following breaking of the blind.

1b) Veterans with co-occurring MDD, who receive active iTBS-TMS, demonstrate significantly greater duration of abstinence in the 6 months following treatment than controls.

Statistical Approach: Exploratory Hypothesis 1b will be tested with Cox regression. The criterion/dependent measure is duration of abstinence after the final iTBS-TMS session. The target predictor and covariates include those for Exploratory Hypothesis 1a.

Exploratory Hypothesis 2

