2a) Cigarette smokers, who receive active iTBS-TMS, demonstrate a significantly lower frequency of relapse over 6 months following treatment than controls (i.e., Veterans with co-occurring smoking who receive sham iTBS-TMS).

Statistical Approach: Exploratory Hypothesis 2a will be tested with binary logistic regression. The criterion/dependent measure is relapse status (abstained or relapsed during the 6 months after last iTBS-TMS session). Treatment group (active iTBS-TMS vs. control) is the target predictor and with current pharmacotherapy for smoking cessation use (binary, yes/no) as a covariate. Education and severity of PTSD, substance use, and/or smoking severity (based on pack-years) will be considered as covariates if, after random assignment, there are post-hoc differences between treatment groups on these variables following breaking of the blind.

2b) Smokers, who receive active iTBS-TMS, demonstrate a significantly greater duration of abstinence over the 6 months following psychosocial treatment than controls.

Statistical Approach: Exploratory Hypothesis 2b will be tested with Cox regression. The criterion/dependent measure is duration of abstinence after final iTBS-TMS session. Treatment group is the target predictor and covariates include those for Exploratory Hypothesis 2a.

Tertiary Analyses

We will concurrently examine the associations between treatment group, multiple neurobiological, neurocognitive and clinical variables (and their potential interactions) and relapse status via an advanced multivariate dynamic longitudinal latent variable modeling framework. However, we are mindful of the proposed sample size, and will avoid building models that risk overparameterization and overfitting.

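### The MDD and smoker analyses fit up to six slopes inside subgroups of unstated size by ordinary likelihood, yet each predicts a significant result

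*Combined protocol and SAP*

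**What the plan says.** Section 8(a) states that "Forty (40) participants are expected to be enrolled", 20 per arm. Section 2(a) describes the randomisation and mentions no stratification by MDD or smoking.

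In the Statistical Analyses Plan, Exploratory Hypothesis 1a predicts that "Veterans with co-occurring MDD, who receive active iTBS-TMS, demonstrate a significantly lower frequency of relapse" than Veterans with MDD given sham. Exploratory Hypothesis 2a predicts that "Cigarette smokers, who receive active iTBS-TMS, demonstrate a significantly lower frequency of relapse over 6 months following treatment than controls", the controls being sham-treated smokers. Both use binary logistic regression. Hypotheses 1b and 2b put the same comparisons to duration of abstinence by Cox regression.

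Treatment is the target predictor throughout. One covariate is fixed: antidepressant use in the MDD models, smoking-cessation medication in the smoker models. Further covariates depend on imbalance seen after unblinding. For MDD, "Education and severity of PTSD, substance use, and/or depressive symptomatology will be considered as covariates"; for smokers the list is the same, with smoking severity in place of depressive symptoms. That makes two to six slopes. No main effect of MDD or smoking and no product term with treatment is listed, so the natural reading is four within-subgroup models, although the text does not state the analysis set.

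For these four analyses the plan gives no subgroup size, small-sample method or multiplicity rule. The Secondary Hypothesis, by contrast, does plan a product term: "We predict an interaction between the specific neuroimaging measure (e.g., Glu level) and treatment group".

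**The concern.** A maximum-likelihood logistic model with several slopes in a fraction of 40 people can separate: some combination of covariates predicts relapse perfectly, and the coefficients have no finite estimate. Short of that, Wald tests become conservative and likelihood-ratio tests reject too often, so the p-value depends on which test the software reports. Because the conditional covariates are chosen after unblinding, the number of slopes is not known in advance either.

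At stake is how the subgroup results are read. Each hypothesis is worded as a significant benefit, and section 3 presents the project as informing VA clinicians who may treat comorbid AUD and depression. A p-value from an unstable fit cannot carry that, whichever way it falls.

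**Working it through.** **Inputs.** N = 40, 20 per arm (sections 2(a) and 8(a)). Relapse: section 1(b) says "At least 60% of those with AUD will experience a major relapse period within 6 months of treatment"; 60% is used for sham, and for both arms under no effect. Slopes: 2 to 6, as counted above.

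**Assumptions.** Subgroup size is not given. Section 2(a) says only that "depressive disorders are highly comorbid in Veterans with AUD", so I take 10 to 30 of 40 (25% to 75%), split evenly between arms in the hand calculations. Two-sided 5% level; active relapse 30% where an effect is needed; no dropout; the fixed binary covariate has 50% prevalence. The plan states no power or effect size, so there is no figure of its own to reproduce.

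**Step 1: information per slope.** Abstainers are the rarer outcome, 0.4n. For n = 16 this is 6.4, giving 6.4/2 = 3.2 per slope with two slopes and 6.4/6 = 1.1 with six. A relapse rate above 60% would make abstainers fewer still.

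**Step 2: a floor for separation.** With treatment alone, the fit fails if either arm has all or no relapses. With m per arm and q = 0.6^m + 0.4^m, the chance is 1 − (1 − q)². For m = 5, q = 0.0778 + 0.0102 = 0.088, giving 16.8%. For m = 8, 12 and 15 it is 3.5%, 0.4% and 0.1%. Covariates add to this.

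**Step 3: the models as planned.** Within-subgroup logistic fits under no effect were simulated, 1,000 trials per setting (Monte Carlo standard error about 1 point at 10%: √(0.1 × 0.9/1000) = 0.009). A fit counts as separated if it is rank-deficient or has fitted probabilities of 0 or 1. Ranges span separate simulations.

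| Subgroup n | Abstainers per slope, 2 / 6 slopes | Separated, 2 slopes | Separated, 6 slopes | LR false positives, 6 slopes |
|---|---|---|---|---|
| 10 | 2.0 / 0.7 | 51% | 89% | 15% |
| 16 | 3.2 / 1.1 | 11–15% | 40–47% | 17.5–23% |
| 24 | 4.8 / 1.6 | 2–3% | 5–10% | 12–13% |
| 30 | 6.0 / 2.0 | under 1% | 1–2% | 9–10% |

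With two slopes the likelihood-ratio false-positive rate is 11%, 8%, 7% and 5% down the column. Wald tests err the other way, rejecting in 0% to 5% of null trials across all settings.

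**Step 4: power within a subgroup.** Power ≈ Φ[(0.3 − 1.96 s₀)/s₁], with s₀ = √(2 × 0.45 × 0.55/m) and s₁ = √((0.24 + 0.21)/m). For m = 8: (0.3 − 1.96 × 0.2487)/0.2372 = −0.79, so 21%. For m = 5, 12 and 15: 15%, 31% and 37%. For the whole trial, m = 20: 48%.

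**Step 5: the remedy.** Firth's method inside the subgroup, without the conditional covariates, removed the instability and held the false-positive rate at about 3–6%.

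**Step 6: what an interaction could show.** Suppose 60% vs 30% holds only in the subgroup and relapse is 60% in both arms elsewhere. The interaction is ln(0.3/0.7) − ln(0.6/0.4) = −1.25. For 16 of 40 its variance is 1/(8 × 0.24) + 1/(8 × 0.21) + 2/(12 × 0.24) = 1.81, so SE = 1.35, |z| = 0.93 and power is about 15%. Across 10 to 30 of 40 it is 13–16%. By ordinary likelihood, with the one fixed covariate and no effect, the all-40 interaction model separates in 28%, 7%, 9% and 30% of trials at n = 10, 16, 24 and 30. By Firth's method, with one extra covariate, no coefficient exceeded 10 in absolute value in 1,000 trials at any of those sizes.

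**The case against.** The hypotheses are labelled exploratory, and section 3 speaks of preliminary data. The subgroups could be large: at 24 to 30 people a two-slope fit rarely separates. Six slopes is a ceiling, since the conditional covariates are only considered if the arms differ. Tertiary Analyses cautions against overfitting and allows for interactions, though it names neither MDD nor smoking. All of this stands, and it makes the point minor and conditional on subgroup size. It does not remove it: with six slopes the likelihood-ratio error is still about 9–10% at 30 people.

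Four stronger readings are tempting. First, a reader might infer that the plan will generate false contrasts between subgroups. It does not test Veterans without MDD or non-smokers, and does not claim that benefit differs. Section 3 does fault earlier trials for not evaluating how smoking affects efficacy, so a reader may draw that inference from the results, but the plan does not. Second, one might say that the interaction planned for the Secondary Hypothesis should replace these models. That hypothesis asks who responds best; these ask whether active beats sham within a population, which is a legitimate and different question. The interaction has little power, and by ordinary likelihood it separates more often than the within-subgroup fit when the subgroup is the majority. Third, one might take it as given that the subgroups are too small to model; the documents give no counts. Fourth, one might extend the instability figures to the Cox models; those were not simulated, and no figure is offered.

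**Conclusion.** The concern holds for the logistic analyses in 1a and 2a, to a degree that depends on an unstated subgroup size. Separation is severe near 10 people, material near 16 and small from about 24 upward with two slopes. The conditional covariates make it worse at every size and leave the likelihood-ratio test anti-conservative across the whole range. For the Cox analyses in 1b and 2b, only the covariate rule and the significance wording are at issue. The figures rest on 60% relapse, a two-sided 5% level, no dropout and subgroups of 10 to 30 of 40; dropout would shrink the subgroups further. Nothing here bears on the primary hypotheses.

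**What to change.** In Exploratory Hypotheses 1a, 1b, 2a and 2b:

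- State that the analysis set is participants with MDD, or smokers, and report the count per arm.
- Drop the covariates that enter on post-hoc imbalance; keep treatment and the one fixed covariate.
- Fit the logistic models by Firth's penalised likelihood.
- Report the active-versus-sham estimate with its 95% confidence interval, and remove the predictions of significance.
- Add, without replacing these models, a treatment-by-MDD and a treatment-by-smoking interaction estimate from all 40, by Firth's method for the logistic model. Make no statement that benefit differs by MDD or smoking without it.

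The cost is SAP wording and minor programming. Enrolment, treatment and data collection are unaffected. The downside is that the interaction estimate will be imprecise, and the report should say so.
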